1.0 TRIAL SUMMARY

Abbreviated Title	Systemic Immune Checkpoint Blockade and Intraperitonea Chemo-Immunotherapy in Recurrent Ovarian Cancer		
Trial Phase	Phase II		
Clinical Indication	Recurrent Platinum Sensitive Ovarian Cancer Patients		
Trial Type	Single arm efficacy trial		
Type of control	Historical comparison control, no control arm		
Route of administration	Intravenous Pembrolizumab, Intraperitoneal Cisplatin, Intraperitoneal Rintatolimod		
Trial Blinding	No blinding		
Treatment Groups	Single arm		
Number of trial participants	45		
Estimated enrollment period	2018-2019		
Estimated duration of trial	5 years		
Duration of Participation	4 years		
Estimated average length of treatment per patient	31 weeks		

2.0 TRIAL DESIGN

2.1 Trial Design

This is a phase II single arm efficacy/safety trial that will evaluate the effectiveness of combining intensive locoregional intraperitoneal (IP) chemoimmunotherapy of cisplatin with IP rintatolimod (TLR-3 agonist) and IV infusion of the checkpoint inhibitor pembrolizumab (IVP) for patients with recurrent platinum-sensitive ovarian cancer (OC).

Patient cohort

This trial will enroll up to 45 patients; eligibility criteria include patients at first or second recurrence previously diagnosed with platinum-sensitive ovarian/fallopian tube carcinoma or primary peritoneal carcinomatosis. Platinum-sensitive OC is defined as patients with a treatment-free interval greater than 6 months. Patients must have at least one peritoneal lesion, measurable by CT/MRI scan. Patients will be allowed if RECIST 1.1 criteria is met for measurable retroperitoneal lesions if there also is the presence of peritoneal lesions during laparoscopy. The lesion should be large enough for biopsy and resection, ideally to yield greater than 2 grams of tumor for immunoassays. If biopsy is insufficient or not feasible during laparoscopy, patients may be allowed to proceed at the discretion of the PI if there are otherwise measurable lesions. All epithelial invasive histologies are included in this phase II design.

Patients will receive a total of six treatment cycles, at 3-week intervals (Schema 1, Section 2.2). We will use an IP neoadjuvant approach, followed by interval cytoreduction (usually laparoscopically) of residual tumor. The decision to perform interval cytoreductive surgery is at

the discretion of the treating physician. Cytoreduction will occur approximately 4 weeks after the fourth treatment cycle. Post-surgery we will consolidate with 2 additional courses of same chemo-immunotherapy regimen. Catheter will be removed 12 weeks after the last treatment. All surgical procedures, if done laparoscopically, are outpatient and will yield up to three serial biopsies of the tumor sites: 1) at catheter placement; 2) at interval cytoreduction which consists of removal of any visible tumor sites and the site biopsied initially whether tumor is present or not; 3) at catheter removal, when site of first tumor biopsy will be re-biopsied for pathologic response.

[figure not shown]
5

We will also obtain serial IP fluid samples, to be collected each time the patient is treated IP and the day after IP therapy. Collection of tumor and IP samples are further detailed below.

Safety Endpoints

Subject safety and tolerability will be monitored continuously using Bayesian methods as detailed in statistical analysis section (Section 8).

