5.1.1 Participant Inclusion Criteria

Participants are eligible to be included in the study only if all of the following criteria apply:

- 1. Patients must be at least 18 years of age on the day of signing informed consent.
- 2. Patients must have first or second peritoneal recurrence of epithelial adenocarcinoma or carcinosarcoma of ovarian, tubal or peritoneal origin:
 - a. Histologic documentation of the original primary tumor is required via the pathology report.
 - b. Original tumor blocks from the primary diagnosis will be requested by our study pathologist at Magee-Women's Hospital of UPMC Cancer Centers if the patient did not have their initial surgery at Magee. Original tumor blocks may be reviewed after registration (informed consent and enrollment). Tumor block should be held until study is completed.
 - 3. Patients must have completed prior platinum-based therapy. Response can be complete or partial if it otherwise meets platinum sensitive criteria, see below.
 - 4. Patients must be platinum-sensitive, defined as having a progression free interval (PFI) of more than 6 months (180 days) from any platinum therapy. Patients are allowed to have had other lines of therapy since last platinum if PFI after platinum therapy meets platinum sensitive criteria.
 - 5. Patients must have measurable disease in the peritoneal cavity, measurable per RECIST 1.1 criteria:
 - a. A mass with a length of 1.0 cm or greater and/or
 - b. A lymph node with a length of 1.5 cm or greater in the shortest axis.

- 6. Patients must be a reasonable candidate for laparoscopy and IP platinum regimen with no prior evidence of clinically significant intra-abdominal adhesions, persistent abdominal wall infections, renal toxicity or bowel obstruction.
- 7. Patients of childbearing potential must:
 - a. Have a negative pregnancy test prior to the study entry.
 - b. Must discontinue breastfeeding prior to the first date of treatment on this study if applicable.
 - c. Agree to follow the contraceptive guidance in Appendix 3 during the treatment period and for at least 120 days after the last dose of study treatment.
- 8. Patients must agree to the protocol designated clinical monitoring to receive the study regimens.
- 9. The participant provides written informed consent for the trial.
- 10. Have an Eastern Cooperative Oncology Group (ECOG) performance status of 0 to 1. Evaluation of ECOG is to be performed within 28 days prior to the date of allocation/randomization.

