5.2 Trial Treatments

The treatment to be used in this trial is outlined below in Table 2.

Table 2 Trial Treatment

Drug	Dose/Potency	Dose	Route of	Regimen/Treatment	Use
		Frequency	Administration	Period	
Cisplatin	50mg/m ²	Q3W	Intraperitoneal	Day 1 of each 3 week cycle	Standard of care
Rintatolimod	200mg	Q3W	Intraperitoneal	Day 2 of each 3 week cycle	Experimental

Drug	Dose/Potency	Dose	Route of	Regimen/Treatment	Use
		Frequency	Administration	Period	
Pembrolizumab	200 mg	Q3W	IV infusion	Day 2 of each 3 week cycle	Experimental

Intraperitoneal Chemotherapy (Institutional Standard of Care)

Catheter placement and diagnostic biopsy

All patients, as part of the clinical care for their disease, will have IP catheters (such as 14-French Bard fenestrated catheter with a subcutaneous reservoir) implanted to allow neoadjuvant and adjuvant chemotherapy and will undergo laparoscopic surgery to obtain tumor biopsies, place the catheter, assess the suitability for IP therapies, and obtain base line peritoneal washes using the same procedure as will be used during IP therapy described below.

The tumor biopsy will be used to confirm tumor histology. If multiple tumor sites exist, multiple samples may be harvested and disease distribution will be noted in the operative note.

The catheter will be subject to standard catheter care based on institutional guidelines.

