7.1.2.6.1 Initial Tumor Imaging

Initial tumor imaging will be performed as part of routine clinical management and must be performed within 28 days prior to the date of IP port placement. Routine imaging includes oral and IV contrasted CT of the chest/abdomen/pelvis. The site study team must review screening images to confirm the participant has measurable disease per RECIST 1.1.

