7.1.2.6.1 Tumor Imaging During the Study

The first on-study imaging assessment should be performed at 7 weeks (49 days ± 7 days) from the IP port placement, again at 13 weeks (91 days ± 7 days) prior to interval surgery, after 4-6 weeks after treatment completion. Subsequent tumor imaging should be performed every 12 weeks (84 days ± 7 days) or more frequently if clinically indicated. After 31 weeks (245 days ± 7 days), participants who remain on treatment will have imaging performed every 12 weeks (84 days ± 7 days). Imaging timing should follow calendar days and should not be adjusted for delays in cycle starts. Imaging should continue to be performed until disease progression is identified by the Investigator.

Objective response should be confirmed by a repeat imaging assessment. Tumor imaging to confirm PR or CR should be performed at least 4 weeks after the first indication of a response is observed. Participants will then return to regular scheduled imaging every 12 weeks, starting with the next scheduled imaging time point. Participants who receive additional imaging for confirmation do not need to undergo the next scheduled tumor imaging if it is less than 4 weeks later; tumor imaging may resume at the subsequent scheduled imaging time point.

Per iRECIST (Section 9.2.1.6), disease progression should be confirmed by the site 4 to 8 weeks after first radiologic evidence of PD in clinically stable participants. Participants who have unconfirmed disease progression may continue on treatment at the discretion of the Investigator until progression is confirmed by the site provided they have met the conditions detailed in Section 9.2.1.6. Participants who receive confirmatory imaging do not need to undergo the next scheduled tumor imaging if it is less than 4 weeks later; tumor imaging may resume at the subsequent scheduled imaging time point, if clinically stable. Participants who have confirmed disease progression by iRECIST, as assessed by the site, will discontinue study treatment. Exceptions are detailed in Section 9.2.1.6.

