The primary endpoint is the objective response rate (rate of CR+PR by RECIST 1.1) at 13 weeks. Based on Ten Tije and Wils et al, the intent-to-treat objective response rate for IP cisplatin alone in platinum-sensitive recurrent ovarian cancer was approximately 45% 51 . An increase from 45% to 65% among response-evaluable patients would be of sufficient interest to warrant further study of the addition of rintatolimod and pembrolizumab in the presence of an acceptable safety profile. An optimal Simon two stage design with $\alpha = \beta = .10$ has been selected that will require 20 patients in the first stage and 25 in the second. In the first stage, 12 patients must have a response (PR or CR) in order to continue to the second stage. If the trial continues to the second stage and accrues 25 more patients and there are 25 or more patients with an objective response among the total of 45 treated, the study will be considered successful at demonstrating increase efficacy compared to cisplatin alone. The probability of early termination if the response rate is 45% is .59.

Continuous Monitoring of RLTs during the Study

Subject safety will be monitored continuously using Bayesian methods. If the posterior probability is .80 or greater that 30% or more of treated subjects experience a treatment related RLT as defined above, the RLT rate would be unacceptable and the study will be suspended pending review by the DSMC. This posterior probability will be calculated from the study's accumulating data and a weakly informative prior distribution. If π denotes a random variable representing the proportion of subjects who will experience a treatment related RLT, we assume π has a beta distribution with parameters a = 1.2 and b = 2.8 which assumes a mean of 30%. The table below describes the number of RLTs per number of treated patients that would trigger suspension. The table also shows the posterior probability that the RLT rate exceeds 33% and the binomial probability associated with the decision for an assumed 33% RLT rate.

Table 8: Number of RLTs per Number of Patients Treated Needed to Trigger Suspension

Subjects	Treatment-Related RLTs	$PP(\pi > 30\%)*$	$Pr(X \ge r p = .30)$
6	4	.903	.070
9	5	.904	.099
12	6	.890	.118
15	7	.880	.131
17	8	.903	.105
20	9	.896	.113
23	10	.891	.197
26	11	.886	.125
29	12	.883	.129
32	13	.880	.133

35	14	.877	.135
38	15	.876	.137
41	16	.874	.138
44	17	.873	.139

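### The baseline CT precedes the laparoscopy at which tumor is sampled, and no rule keeps a sampled lesion out of the RECIST target set, so tissue removal can add to apparent response

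*Combined protocol and SAP*

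**What the plan says.** - **Endpoint.** Section 8.1: "The primary endpoint is the objective response rate (rate of CR+PR by RECIST 1.1) at 13 weeks". Success is 25 or more responders among 45, against a historical 45%, with no control arm.
- **Baseline scan.** The Initial Tumor Imaging section says that this scan "must be performed within 28 days prior to the date of IP port placement".
- **Sampling.** Section 5.2 says that all patients "will undergo laparoscopic surgery to obtain tumor biopsies, place the catheter". Section 2.1 requires this of the disease: "Patients must have at least one peritoneal lesion, measurable by CT/MRI scan". Shortly afterwards it says: "The lesion should be large enough for biopsy and resection, ideally to yield greater than 2 grams of tumor for immunoassays".
- **Next scan.** The section on imaging during the study says: "The first on-study imaging assessment should be performed at 7 weeks". Time is counted from port placement, and a second scan follows at 13 weeks. The flow chart in Section 6.1 shows no CT between laparoscopy and cycle 1.
- **Size to qualify.** Section 5.1.1, criterion 5: "A mass with a length of 1.0 cm or greater and/or" a lymph node of at least 1.5 cm.
- **Target lesions.** Section 7.1.2.6.3 allows up to 10 targets, 5 per organ. Neither that section, Appendix 4 nor Section 8 says what to do with a lesion sampled at port placement. Section 3.3 only has the biopsy site marked with a clip.
- **Exception.** Section 2.1 also says: "Patients will be allowed if RECIST 1.1 criteria is met for measurable retroperitoneal lesions", provided peritoneal lesions are present at laparoscopy.

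**The concern.** Response is change from baseline in the sum of target-lesion diameters. If a target loses tissue to the surgeon after the baseline scan and before the first dose, the week 7 and week 13 scans attribute that loss to treatment. Sampling can only make a lesion smaller, so the error runs towards response. A randomised comparison would carry the same error in both arms. Here the comparison is with a fixed 45%, so nothing offsets it. At stake is whether a result close to the 25-of-45 threshold can be read as drug activity.

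**Working it through.** **1. The plan's own design.** Inputs from Section 8.1: p0 = .45, p1 = .65, stages of 20 and 25, success at 25 or more of 45, stated probability of early termination (PET) .59 at 45%. With stage 1 cut c,

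P(success | p) = Σ over x = c to 20 of P(X1 = x) × P(X2 ≥ 25 − x), where X1 ~ Bin(20, p) and X2 ~ Bin(25, p).

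| Stage 1 cut | PET at 45% | P(success) at 45% | Power at 65% |
|---|---|---|---|
| 12 of 20 (as written) | .869 | .053 | .746 |
| 10 of 20 | .591 | .090 | .900 |

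The stated PET of .59 and α = β = .10 match a cut of 10, not the written 12. That is a separate discrepancy. Both cuts are carried below so that this point does not depend on how it is resolved.

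**2. Size of the artefact in one lesion.** Assumptions, none of them in the documents: density 1 g/mL, spherical lesion, uniform shrinkage, all tissue from one lesion, the usual 30% fall for PR, and no regrowth by week 13.

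Mass of a lesion of diameter D cm: m = (π/6)D³ g. Fall in diameter after removing w g: 1 − ((m − w)/m)^(1/3), or 100% if w ≥ m.

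A fall of 30% needs (m − w)/m = 0.7³ = 0.343, so m = w/0.657.
- w = 2 g: m = 3.04 g, D = (6 × 3.04/π)^(1/3) = 1.80 cm (1.74 to 1.83 cm for densities of 1.10 to 0.95 g/mL).
- w = 1 g: m = 1.52 g, D = 1.43 cm.

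A 2 g sphere is (12/π)^(1/3) = 1.56 cm across. A 1.0 cm sphere weighs only 0.52 g and cannot yield 2 g.

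| Sole target, D | Mass | Fall if 2 g removed | Fall if 1 g removed |
|---|---|---|---|
| 1.5 cm | 1.77 g | 100% | 24.3% |
| 2.0 cm | 4.19 g | 19.5% | 8.7% |
| 2.5 cm | 8.18 g | 8.9% | 4.2% |
| 3.0 cm | 14.14 g | 5.0% | 2.4% |
| 4.0 cm | 33.51 g | 2.0% | 1.0% |

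Removal also adds to any partial drug effect. After a 19.5% loss, a 2.0 cm lesion needs only a further 1 − 0.70/0.805 = 13% to reach 30%. With several targets the loss is spread over the whole sum of diameters.

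**3. Effect on the decision rule.** Let f be the share of true non-responders scored as responders because of sampling. The apparent rate at a true 45% is .45 + .55f. The documents give no value for f, so these are assumed values.

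| f | Apparent rate | P(false success), cut 12 | P(false success), cut 10 |
|---|---|---|---|
| 0 | .450 | .053 | .090 |
| 2% | .461 | .070 | .117 |
| 5% | .4775 | .101 | .165 |
| 10% | .505 | .171 | .270 |

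In patients: at a true 45%, 45 × .55 = 24.75 are non-responders, so f = 5% is about 1.2 patients and f = 10% about 2.5.

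**The case against.** A reader might infer that the protocol has the surgeon resect over 2 g from the measured lesion in every patient at entry. The documents do not support that.

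- **The amount is an aim.** Section 2.1 uses the word ideally. It names both biopsy and resection, and elsewhere these are separate events. Sections 3.1 and 3.3 contrast the original biopsy with tumors resected later, and removal of visible tumor belongs to interval cytoreduction, after the week 13 scan. Section 3.3 also plans to compare tumor dimensions between first and second surgery, which presupposes tumor left in place. Against this, the next sentence of Section 2.1, on insufficient biopsy, refers to laparoscopy and fits the entry procedure. The text is ambiguous.
- **The sampled lesion need not be the measured one.** The sentence before the 2 g aim admits patients measurable only retroperitoneally. In them the peritoneal lesions seen at laparoscopy are not the measured disease, and the artefact does not arise.
- **Tissue may come from several sites.** Section 5.2 allows this. Small samples do little: 0.5 g from a 1.5 cm lesion is a 10.5% fall and 0.2 g is 3.9%, although 0.5 g would still remove most of a 1.0 cm lesion.

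A second tempting inference is that the trial's false-positive rate exceeds .10. That depends on f, which is assumed, and on the stage 1 cut. Under the written 12-of-20 rule, f = 2% stays well below .10 and f = 5% only just reaches it.

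These points limit how often and how strongly the artefact acts. They do not supply the missing rule: the order of scan, sampling and scan is fixed, and a sampled lesion may still be a target.

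**Conclusion.** The gap is real and its direction is certain, but its frequency is unknown. As written, the plan lets tissue taken at port placement count towards RECIST shrinkage in the single-arm primary endpoint. It matters mainly for a small sole or dominant target: up to about 1.8 cm if 2 g comes from that lesion, about 1.4 cm if 1 g does, with partial help to response somewhat above those sizes. It is minor at 3 cm and beyond. The size limits rest on the density, shape, single-lesion and 30% PR assumptions. The false-success figures illustrate sensitivity to f and do not estimate the trial's error rate. The documents support neither a claim that responses will be manufactured routinely nor a claim that alpha is already breached. A clarification is worth making because one or two misscored patients would matter near the threshold.

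**What to change.** In Section 7.1.2.6:

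1. Finalise target lesions on the baseline CT after laparoscopy and before the first on-study scan, using the operative record of which lesions were sampled.
2. Do not use a lesion biopsied or resected at port placement as a target when another measurable lesion exists.
3. When it is the only measurable lesion, keep it as the target and flag the patient.

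In Section 8.2, prespecify a sensitivity analysis of the response rate and the success rule in which flagged responders count as non-responders. Report it beside the primary result and label it a conservative lower bound. It errs in the opposite direction, so it should not replace the primary analysis.

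Cost: a few sentences, one extra analysis, and an entry linking each sampled site to its CT lesion. No extra scans, and no change to sample size or biopsy practice. The downsides are that in some patients a sampled lesion is lost as a target, and that the lower bound discards some true responses.

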2.2 Trial Diagram

Schema 1. Trial design and treatment schedule diagram. Horizontal line represents time in weeks. The schedule for blood, tumor tissue and IP fluid collection is detailed in the text.

3.0 OBJECTIVE(S) & HYPOTHESIS(ES)

3.1 Primary Objective(s) & Hypothesis(es)

(1) **Objective:**

This phase II trial will consist of up to 45 evaluable patients to specifically define the clinical efficacy and impact on immunologic efficacy endpoints of IP cisplatin/rintatolimod and IV pembrolizumab. Primary clinical efficacy endpoint will be objective response rate by RECIST

6

1.1 criteria at 13 weeks (CT imaging at 7 weeks and 13 weeks) as compared to historical controls. The trial schema encapsulates a trial design similar to our recent phase I SPORE trial (UPCI 11-128/NCT02615574, [name] - Clinical PI; [name]- Translational PI) in which intraperitoneal cisplatin and rintatolimod was well tolerated and induced favorable immune response on interim analysis.

The strategy of combining pembrolizumab with IP cisplatin/rintatolimod is to induce cell death and cell damage of the peritoneal tumor implants with chemotherapy followed by locoregional and systemic modulation of innate and adaptive immune effectors to further promote immune clearance of remaining tumor.

Objective/Pathologic Response

Imaging will be performed at baseline, two weeks after cycle 2 and cycle 4 for objective responses by RECIST 1.1 criteria. Imaging will again be performed 4-6 weeks after completion adjuvant chemotherapy for baseline post treatment. Between 2 months after successful completion of the trial, the IP port will be removed laparoscopically. During the IP port removal, a second-look treatment effect evaluation and biopsy for pathologic response will be performed.

Disease Progression

Progression during trial will be assessed by iRECIST. If there is confirmed progression prior to interval surgery, patients will not undergo interval surgery, just IP port removal and biopsy after confirmed progression by iRECIST. Patients will be followed for 3 years or until recurrence after completing treatment to determine time to progression (TTP), ratio of progression-free interval (PFI) as compared to their initial PFI, and survival will be a secondary efficacy endpoint. Follow-up data will be used to estimate progression-free and overall survival at 3 years.

Biological Endpoints

We will characterize the immune response changes in each patient as measured by the total number of tumor-infiltrating CD3+CD8+ T cells (TILs) with the baseline evaluation of initial laparoscopic tumor biopsy when IP catheter is placed compared to interval surgical samples and laparoscopic biopsy at time of IP catheter removal. Changes in the frequency of T cells in the peritoneal washes at each cycle will also be evaluated. Since measurements of intra-patient changes in intra-tumoral CD8+ T cells before and after chemotherapy with chemokine modulation (in solid fraction of the tumor), as the primary endpoint of efficacy, were perceived as less reliable due to the difficulties in the longitudinal sampling of "representative" parts of tumor when comparing the original tumor biopsy to the resected tumors, and likely heterogeneous impact of chemotherapy on different parts of the tumors (resulting in the variations in immune infiltrates), such solid tumor evaluations will be performed as correlative studies and compared with the immune cell changes in the peritoneal fluid (which composition has also been shown to be predictive for the long-term outcomes in OC1. Frequent flushing of

the peritoneal catheter is standard of care at our institution to maintain catheter patency and assess for locoregional toxicity. It also allows collection of peritoneal samples.

7

Hypothesis:

We postulate that a treatment regimen that combines induction of locoregional immunogenic cell death using cisplatin and immune modulation through TLR-3 activation combined with immune checkpoint blockade via systemic anti-PD-1 which induces increased TILs and an improved anti-tumor T cell response. To test this hypothesis, we propose to:

- 1. Perform phase II clinical trial of combination IP cisplatin/rintatolimod chemoimmunotherapy plus IV pembrolizumab with efficacy clinical endpoints.
- 2. Identify the impact of combination treatment on the tumor immune microenvironment. This aim will evaluate the ability of the treatment to promote TIL accumulation, modulate biomarkers of immune exhaustion, and induce genes associated with cytotoxic anti-tumor immunity.

